## **Visit 8** (12 months of age; day $365 \pm 14$ days):

All participants will have a physical examination (including weight and length measurements) and will receive measles vaccine as per EPI.

All participants: next visit will be scheduled.

# Visit 9 (15 months of age; day 450 ± 14 days):

All participants will have a physical examination (including weight and length measurements) and will receive Hexaxim® vaccine as per EPI.

All participants will receive benefit vaccine (Hepatitis A or Varicella).

A nasopharyngeal swab will be taken from all participants prior to vaccine administration for culture/ PCR detection of PCR serotypes.

All participants: next visit will be scheduled.

# Visit 10 (18 months of age; day $540 \pm 14$ days):

All participants will have a physical examination (including weight and length measurements).

All participants will have a blood draw for ELISA for vaccine serotypes (end of study).

A nasopharyngeal swab will be taken from all participants for culture/ PCR detection of PCR serotypes.

Study termination visit.

Protocol: PCV1+1, version 2.120 Protocol date: 6th February 2017

Visit number 1 2 3 4 5 6 7 8 9 10 12 months 15 months 6 weeks 10 weeks 14 weeks 18 weeks 6 months 9 months 10 months 18 months Age Age (days) V1+28-35 V2 +28-35 V3 [contact] ±14 Dav 42-56  $180 \pm 14$ 270 ±14 V6+28-35  $365 \pm 14$  $450 \pm 14$ ICF signed Х Inclusion/ Х exclusion criteria Medical history Х Physical Х Х Х Х Х Х Х Х Х Х examination Х Randomisation PCV10^2 PCV10^2 Grp 1a (PCV10) Grp 1b (PCV13) PCV13 PCV13 Blood draw: Serum for ELISA Х Х Х Х Х of PCV vaccine serotypes (3ml) Blood draw: Serum for PCV Х Х OPA in subset (2ml) Blood draw: EPI# Х Х Х Х Х Hexaxim®3 Х Rotavirus Х Х vaccine Х Х Measles vaccine Varicella or Hepatitis A Х vaccine NP swab Х Х Х

**Table 2a:** Study Schedule of Events including the time points at which blood will be obtained by vecupuncture for analysis of the immuno genicity endpoints, and nasopharyngeal swabs collected for evaluation of colonization: **Group 1 (1+1, 6 weeks)** 

: Refers to vaccination with respective PCV13 or PCV10 vaccine to which randomized. All children will receive the same PCV formulation as the primary series as a booster dose. Provided as standard of care in the public immunisation program, per indicated time points. Proposed vaccine to all children as a potential benefit for study participation. Participants whose randomization number ends in an even number will receive Hepatitis A vaccine and those with an odd number the Varicella vaccine.  Serum samples taken for ELISA of the vaccine serotypes.  serum sample taken for opsonophagocytic activity (OPA) which will be tested for in a subset of patients. Naspharyngeal (NP) swab taken using a flocked swab and transported in STGG medium, for culture/PCR detection and serotyping. #Blood draw for antibody testing of vaccine preventable diseases included in EPI

> Protocol: PCV1+1, version 2.121 Protocol date: 6th February 2017

Table 2b: Study Schedule of Events including the time points at which blood will be obtained by vecupuncture for analysis of the immuno genicity endpoints, and nasopharyngeal swabs collected for evaluation of colonization: Group 2 (1+1, 14 weeks)

Visit number	1	2	3	4	5	6	7	8	9	10
Age	6 weeks	10 weeks	14 weeks	18 weeks	6 months	9 months	10 months	12 months	15 months	18 months
Age (days)	Day 42-56	V1+28-35	V2 +28-35	V3 [contact] ±14	270 ±14	V6 [contact] ±14	450 ±14	540 ±14
ICF signed	Х									
Inclusion/	Х									
exclusion criteria										
Medical history	Х									
Physical examination	Х	Х	Х	Х	Х	Х	Х	Х	Х	Х
Randomisation	Х									
Grp 2a (PCV10)			PCV10 			PCV10 				
Grp2b (PCV13)			PCV13 			PCV13 				
Blood draw: Serum for ELISA of PCV vaccine serotypes  (3ml)	х			Х		х	х			Х
Blood draw: Serum for PCV OPA in subset  (2ml)	Х						х			
Blood draw: EPI#	Х					Х				
Hexaxim® 	Х	Х	Х						Х	
Rotavirus vaccine 	Х		Х							
Measles vaccine 					Х			Х		
Varicella or Hepatitis A vaccine⁴									х	
NP swab 						Х			Х	Х

Table 2c: Study Schedule of Events including the time points at which blood will be obtained by vecupuncture for analysis of the immuno genicity endpoints, and nasopharyngeal swabs collected for evaluation of colonization: Group 3 (2+1)

Visit number	1	2	3	4	5	6	7	8	9	10
Age	6 weeks	10 weeks	14 weeks	18 weeks	6 months	9 months	10 months	12 months	15 months	18 months
Age (days)	Day 42-56	V1+28-35	V2 +28-35	V3 [contact] ±14	270 ±14	V6 [contact] ±14	450 ±14	540 ±14
ICF signed	Х									
Inclusion/ exclusion criteria	Х									
Medical history	Х									
Physical examination	Х	Х	Х	Х	Х	Х	Х	Х	Х	Х
Randomisation	Х									
Grp 3a (PCV10)	PCV10 		PCV10 			PCV10 				
Grp3b (PCV13 EPI)	PCV13 		PCV13 			PCV13 				
Blood draw: Serum for ELISA of PCV vaccine serotypes (3ml)	Х			х		х	х			х
Blood draw: Serum for PCV OPA in subset (2ml)	х						x			
Blood draw: EPI#	Х					Х				
Hexaxim® 	Х	Х	Х						Х	
Rotavirus vaccine 	Х		Х							
Measles vaccine 					Х			Х		
Varicella or Hepatitis A vaccine⁴									х	
NP swab 						Х			Х	Х

#### Laboratory methods

The laboratory tests will be undertaken at RMPRU and its collaborator.

#### Immunogenicity assays:

The volume of blood collected from each participant at enrolment, at one month following the 1st dose in the 1+1 arms (Groups 1a, 1b, 2a, 2b) and following the 2nd dose in the 2+1 arms (Groups 3a and 3c) will be approximately 3ml. In addition, at one month following the booster dose and at 18 months of age, an additional 5ml of blood will be collected. Each sample will be labeled with a unique laboratory coded number, so that laboratory personnel will be blinded to the participant identify and randomization. Clotted blood samples will be delivered to the RMPRU laboratory within 4 hours of collection, centrifuged and the serum aliquoted and stored at -70°C until ready for testing. Residual serum samples will be stored for future testing, including assessing immune response to other administered vaccines. The participant's parent/legal guardian may decline to have the sample tested for any other reason than requested for this study, and also to have the sample destroyed at any time.

#### ELISA assay for serotype-specific IgG concentrations

Serotype specific antibody concentrations will be undertaken in all participants for all pneumococcal serotypes (1, 3, 4, 5, 6A, 6B, 7F, 9V, 14, 18C, 19A, 19F, and 23F) included in PCV13, to avoid the laboratory staff being unblinded as to which arm the child might have been allocated to. Samples will be tested at the RMPRU laboratory, using standardized methods and reference sera as recommended by WHO. The ELISA assays will be undertaken in samples obtained one-month following the 1st dose in Groups 1 and 2, and one month following the 2nd dose in Groups 3a and 3b. In addition, ELISA will be performed on samples obtained one-month after the booster dose of PCV (10 months of age) and at 18 months of age.

#### OPA assays to the 13 pneumococcal serotypes

The OPA assays will be undertaken at the WHO pneumococcal assay Reference Laboratory of [name] (London, United Kingdom).

A random sample of 20% of enrolled cases (n=20) will be tested from each of the study arm using blood samples obtained from one-month following the booster dose of PCV.

#### Antibody titres against vaccine preventable diseases

Antibody titres to diphtheria-toxoid, tetanus toxoid, anti-FHA, anti-PT and anti-Hepatitis B surface antigen will be evaluated using a multiplex assay on the Luminex platform at the RMPRU. Measles antibody will be measured by standard ELISA assay using commercially available

> Protocol: PCV1+1, version 2.124 Protocol date: 6th February 2017

assays. Assays testing for rotavirus IgA and IgG will be set-up at the RMPRU, in collaboration with the diarrheal laboratory at Centre for Disease Control and Prevention; USA.

# Nasopharyngeal swabs for pneumococcus identification/ culture and serotyping

Nasopharyngeal swabs will be collected using a flocked swab at 9, 12 and 18 months of age. The samples will be stored in STGG medium until tested. The first line testing will use standard culture methods and serotyping per established methods recommended by WHO.

# Safety monitoring

The study will undertake passive surveillance for hospitalizations of study participants, including for pneumonia and invasive pneumococcal disease, throughout the study. A Data and Safety Monitoring Board (DSMB) will be established to review whether any of the hospitalizations are possibly due to pneumococcal disease (with a specific focus on IPD and radiologically confirmed pneumonia) and determine whether there is any trend to an excess of cases in any of the 1+1 dosing arms compared to the 2+1 dosing arm. Summary reports of all hospitalizations, radiologically confirmed pneumonia and IPD (including serotype data) will be provided to the DSMB on a quarterly basis, and more frequently if requested. The incidence (per 100,000) of PCV13 vaccine-serotype IPD among HIV-unexposed children in 2012 in Soweto was 20.6, 0, 5.6 and 0 in age groups <10 weeks, 10 wks to 6 months, 6.1-12 months and 9-12 months of age, respectively. As such no cases would be expected in a sample size of 600 participants, a hold on further enrolment into the study will, however, be implemented if there are more than three cases of PCV13 serotype IPD across any of the 1+1 dosing schedules if occurring at least 4 weeks after receipt of the first dose of PCV in that group. The DSMB will determine whether the study should then be discontinued. If the study is discontinued all the children in the 1+1 dosing arms will default to a 2+1 dosing schedule if age appropriate or receive another dose of PCV as required. The DSMB will also be tasked with evaluating the post-booster data from the study, to determine whether the children in any of the 1+1 dosing arm should be offered an additional dose of PCV in the presence of significant inferior immune responses to the PCV schedule

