- 4. A further factor to consider is that timing of the 1st dose of PCV may differentially impact on the immunogenicity of the vaccine. This could result from lower concentrations of maternal-derived transplacentally- acquired serotype specific capsular antibody with increasing age, which too could dampen the immune response to the first dose of PCV, the closer it is given to birth. Furthermore, maturation of the immune system in the first few weeks of life could theoretically result in heightened immunogenicity to the single dose of PCV when administered at 14 instead of 6 weeks of age. Also, theoretically priming of the immune system with diphtheria toxoid vaccine at 6 weeks of age could heighten the immune response of CRM197 constituted PCV when the first dose is iven at 14 weeks, rather than at 6 week of age. Considering the inherently reduced risk of pneumococcal disease during the first few months of life because of the current low risk of colonization by vaccine-serotypes, delaying PCV vaccination from 6 to 14 weeks of age is unlikely to significantly increase susceptibility to pneumococcal disease.
- 5. Also, the immune response following a booster dose after a single primary dose of PCV could be higher compared to after a two-dose primary series. That lower vaccine antigen exposure during the primary series can accentuate the immune responses to a booster dose of conjugate vaccine, is supported by studies on *Haemophilus influenzae* type b conjugate vaccine (HibCV). In a study looking at alternate HibCV dosing concentrations in South Africa, children who received a 1/10th of the approved dose of HibCV had greater antibody responses following the booster dose of vaccine compared to those who received the full-strength dose .

In view of the above, a study is underway in the United Kingdom, to evaluate whether the country can transition from a 2+1 to 1+1 PCV dosing schedule. This is undertaken with supporting evidence of reduced circulation of the commonly colonizing PCV serotypes 3-4 years after routine

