### Trial visit details

#### Visit 1 (6 weeks of age, day 42-56 of life):

For all participants, informed consent will be signed, inclusion and exclusion criteria reviewed, medical history will be collected and physical examination (including weight and length measurements) and randomization will be performed.

Blood draw for testing of baseline antibody concentrations against vaccine preventable diseases All participants will receive Hexaxim® and Rotavirus vaccine as per EPI.

Group 1 & 3 participants will also receive PCV10/ PCV13 (as per randomisation).

All participants will receive a visit appointment card, and the next visit will be scheduled.

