#### Visit 2 (10 weeks of age; 28-35 days post visit 1):

All participants will have a physical examination (including weight and length measurements) and will receive Hexaxim® vaccine as per EPI.

Group 1 participants will have a blood draw for ELISA for PCV vaccine serotypes (28-35 days post vaccine administration).

All participants: next visit will be scheduled.

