## Visit 3 (14 weeks of age; 28-35 days post visit 2):

All participants will have a physical examination (including weight and length measurements) and will receive Hexaxim® and Rotavirus vaccine as per EPI.

Group 2 & 3 participants will also receive PCV10/ PCV13 (as per randomisation).

All participants: next visit will be scheduled.

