### Protection of human research participants

The major risk to the study participants relate to those included in the 1+1 dosing schedule, whose risk for disease might be slightly increased due to sub-optimal immune responses to the dosing schedule compared to those who receive the 2+1 dosing schedule. The incidence (per 100,000) of PCV13 vaccine-serotype IPD among HIV-unexposed children in 2012 in Soweto, South Africa was 20.6, 0 and 5.6 in age groups <10 weeks, 10 weeks to 6 months and 6.1-12 months of age, respectively. As such, no cases would be expected in a sample size of 600 participants. Considering that the circulation of the vaccine-serotype is likely to have decreased even further since 2012, we expect this risk of vaccine-serotype IPD also to have declined since 2012. Recent South African data comparing post-vaccine (2015) and pre-vaccine years (2005-2008), indicates that the overall IPD incidence (per 100,000 population) declined from 9.9 cases prior to PCV immunisation to 4.4 in 2015, including a PCV7-serotype decline of 87%; and PCV13-serotype (additional 6 serotypes) IPD declined of 75%. In tandem, there was a significant increase in nonvaccine-serotype IPD of 18% (95%CI:11% - 24%). Among children <2 years IPD rates declined by 97%, including a 93% reduction in PCV13-serotype IPD. Non-vaccine serotypes increased significantly only in the 45—64 year old (39%; 95%CI:28%, 49%) and >64 years age groups (56%; 95%CI:38%,69%). The predominant non-vaccine serotypes in 2015 were serotypes 12F (82/447, 18%) and 8 (16/99, 16%), neither of which are included in PCV10 or PCV13.

Furthermore, excluded from this study are children born to HIV-infected women, who are at increased risk of pneumococcal disease, even though the incidence of vaccines-serotype IPD in HIV-infected children has declined by >80% since the early 2000s. Also, it is unlikely that vaccinating 600 (2.0%) of the annual birth cohort of 28,000 in Soweto would have any impact on the community wide transmission of the vaccine-serotypes.

To offset the above marginal increased risk of severe vaccine-serotype IPD (incidence <10/100,000 in children <2 years age), the study will offer all study participants a single dose of either varicella or hepatitis A vaccine, neither of which are included in the current public immunisation program. The exact choice of vaccine will be finalized based on its availability in South Africa.

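### The automatic enrolment hold starts counting IPD 84–98 days after randomisation in the 14-week arms, against 28 days in the 6-week arms, so it cannot register a case during the delay that defines the 14-week schedule

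*Protocol*

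**What the plan says.** Protocol, Safety monitoring: "a hold on further enrolment into the study will, however, be implemented if there are more than three cases of PCV13 serotype IPD" across the 1+1 schedules, and a case counts only "if occurring at least 4 weeks after receipt of the first dose of PCV in that group". The DSMB then decides whether the study stops.

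The visit descriptions fix when that clock starts:

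- "Visit 1 (6 weeks of age, day 42-56 of life": "Group 1 & 3 participants will also receive PCV10/ PCV13 (as per randomisation"). Group 2, the 14-week 1+1 schedule, gets no PCV here.
- "Visit 2 (10 weeks of age; 28-35 days post visit 1"): no PCV in any group.
- Visit 3, 28–35 days after Visit 2: "Group 2 & 3 participants will also receive PCV10/ PCV13 (as per randomisation"). This is Group 2's first dose.

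Two other passages bear on the interval. Introduction and background (item 4) reasons that "delaying PCV vaccination from 6 to 14 weeks of age is unlikely to significantly increase susceptibility to pneumococcal disease". Protection of human research participants names possibly weaker protection under 1+1 dosing as the main risk to participants.

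Other monitoring has no post-dose window. Surveillance for hospitalisations runs throughout the study. The DSMB receives quarterly summaries of all hospitalisations and IPD and looks for an excess in any 1+1 arm over the 2+1 arm (Safety monitoring). Every IPD case is reported within 24 hours (SAE Reporting Requirements for this Study).

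**The concern.** What sets the 14-week schedule apart is that the infant has no PCV between Visit 1 and Visit 3, while the 2+1 infant has had a dose. Because the hold's clock starts from the first dose in the child's own group, the rule excludes that interval by construction, together with the four weeks after it. The protocol assumes that the delay adds little risk, and its one pre-set numeric trigger cannot react if the assumption fails.

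The two 1+1 schedules are also counted over different age ranges, although their cases feed the same rule. At stake is whether an unexpected cluster in PCV-free infants would pause enrolment automatically, or only if someone chose to act on it.

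**Working it through.** **1. The plan's own figure: no cases expected in 600.** The stated 2012 rates per 100,000 are 20.6 (under 10 weeks), 0 (10 weeks to 6 months) and 5.6 (6.1–12 months). No time unit is given. I assume child-years, and take reading the rate as a risk per child as the upper bound. Ten weeks is day 70, and 6 months is taken as day 182.

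- To 12 months, enrolled at day 42: 600 × (20.6 × 28 + 0 + 5.6 × 183) / (365.25 × 100,000) = 0.026.
- Adding the protocol's bound of 10 per 100,000 from day 365 to day 540: 600 × 10 × 175 / (365.25 × 100,000) = 0.029, total 0.055.
- As risk per child: 600 × (20.6 + 0 + 5.6) / 100,000 = 0.157.

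All are well below 1, so the statement reproduces.

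**2. When counting starts.**

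| | 6-week arms (Group 1) | 14-week arms (Group 2) |
|---|---|---|
| First dose, days after Visit 1 | 0 | (28–35) + (28–35) = 56–70 |
| Count starts, days after Visit 1 | 0 + 28 = 28 | 84–98 |
| Age when count starts, days | 42–56 + 28 = 70–84 | 42 + 84 = 126 to 56 + 98 = 154 |

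The 56–70 PCV-free days in Group 2 are all uncounted. The stretch uncounted in Group 2 only runs from 28 days after Visit 1 to 84–98 days after it, which is 56–70 days.

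**3. How much time that is.** Follow-up from day 42 to day 540 is 498 days.

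- Group 2: 84/498 = 17% to 98/498 = 20% uncounted. Group 1: 28/498 = 6%.
- A hold on enrolment matters only while enrolment is open, planned as 12 months (Study Design). Assuming uniform accrual over 365 days, the share of on-study time before closure that falls in an uncounted first w days is 1 − ((365 − w)/365)². For w = 84 this is 41%, for w = 98 it is 46%, and for w = 28 it is 15%.

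**4. Expected cases in Group 2's excluded window (200 infants).**

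- Stated rates per child-year: 200 × 20.6 × (14 to 28) / (365.25 × 100,000) = 0.002–0.003. All of this falls before day 70. The Group 2-only stretch contributes 0.
- 20.6 applied to the full 84–98 days: 0.009–0.011.
- 20.6 as risk per child: 200 × 20.6 / 100,000 = 0.041.

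For four cases to be expected in 84 days the rate would have to be 4 / (200 × 84 / 365.25) = about 8,700 per 100,000 child-years, some 420 times 20.6.

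**5. Effect on the trigger (400 1+1 infants, Poisson).**

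| Rates | Expected, window as written | Expected, from enrolment | P(more than 3), as written | P(more than 3), from enrolment |
|---|---|---|---|---|
| Stated, then 10 per 100,000 after 12 months | 0.030 | 0.037 | 3 × 10⁻⁸ | 7 × 10⁻⁸ |
| Flat 20.6 throughout | 0.100 | 0.112 | 4 × 10⁻⁶ | 6 × 10⁻⁶ |

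**The case against.** The strongest reply is that nothing is hidden and almost nothing is expected. The DSMB sees all IPD, compares each 1+1 arm with the 2+1 arm without any post-dose window, and may ask for reports more often. At the protocol's rates the two counting rules behave alike. A lag after dosing is also a recognised way to count disease after vaccination. No figure in the protocol is wrong on this point.

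Most of this stands and limits the size of the point. It does not remove it, for three reasons:

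- Near-zero expectation applies equally to the counted window. The sponsor still wrote a trigger, as a guard against the unexpected.
- The remaining safeguards are discretionary. The Monitoring section has the DSMB meeting annually, against a 12-month enrolment, and has the protocol team reviewing data pooled across arms, in which a Group 2 excess would not show.
- A post-dose lag has a rationale where the dose comes at entry. In Group 2 the absence of a dose is part of what is being studied.

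A reader might infer more than the documents support:

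- *That the rule misses the riskiest age in the 14-week arms only.* The protocol says incidence "was 20.6, 0 and 5.6 in age groups <10 weeks, 10 weeks to 6 months and 6.1-12 months of age, respectively". The on-study part of the under-10-week band ends at day 70, within the first 28 days after Visit 1, and is equally uncounted in the 6-week arms. A case at 8 weeks of age would count in neither schedule. The Group 2-only stretch (from day 70–84 to day 126–154) lies in the band with stated incidence 0. That zero is a 2012 rate, after PCV entered the public programme in 2009. If most of those infants were offered an early dose, it says little about PCV-free infants, but it does not show raised risk.
- *That the trial sets out to show the delay is safe.* Study Design aims at non-inferior post-booster immune responses. Adverse events, including IPD, are a secondary outcome, and the low risk of the delay is a background argument.
- *That the cases are lost.* Only the automatic count omits them.

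**Conclusion.** The point holds as a moderate gap in the logic of one rule. The hold count starts 84–98 days after randomisation for 200 of the 400 1+1 infants and at 28 days for the other 200. It cannot register any case while the 14-week infants lack the dose that the 2+1 infants have had. This sits badly with the protocol's assumption about the delay and with the risk it names as the main one.

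The expected numerical effect is negligible: at most about 0.04 excluded cases, and a chance of reaching the threshold that stays far below 1 in 10,000 under either window. The gap matters only for an unexpected excess. The conclusion rests on reading the clause as the first PCV dose of the child's own arm, on the stated visit windows, and, for expected counts only, on the assumed time unit of the incidence.

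**What to change.** Reconcile the counting window in Safety monitoring with Introduction and background (item 4) and Protection of human research participants:

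- Start the hold count at the same point after randomisation in every 1+1 arm, so that Group 2 cases before and shortly after the first dose are included. Counting from randomisation covers the whole PCV-free interval. A common lag after Visit 1 would also align the arms, but leaves that lag uncounted in all of them. The protocol should state which is used.
- Leave the threshold as it is.
- Show the DSMB pre-first-dose and post-first-dose cases as separate lines, by arm.

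The cost is one sentence in the protocol and a matching line in any DSMB charter. No new data are needed, since every IPD case is already reported within 24 hours. The downside is that a few early cases that no schedule could have prevented may count. The DSMB can weigh these, and working step 5 shows that the chance of an unwarranted hold stays negligible.
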